- 4) After a woman provides verbal consent over the phone, she will be prompted to do the electronic HIPAA form at the time of the second online survey.
- 5) Once the consent and authorization are given, the woman is eligible for the rest of the study.
 - a. A reminder call will be made if the first online survey is not completed within 2 weeks. A refusal postcard will be sent if she cannot be reached.
- 6) Depending on the randomization of group:
 - a. Those receiving TIWeb only, the TIWeb information will be mailed and emailed out within 1 week of receiving the consent and authorization.
 - b. Those receiving the cancer screening call, the RA will begin attempting 1 week after receiving the consent and authorization.
 - c. Those receiving the TIWeb and call, the TIWeb information will be mailed and emailed within 1 week of receiving the consent and authorization. The call will then be attempted 1 week after the mailing of the TIWeb information.
- 7) Data collection calls or electronic communications will be placed at 4 weeks and 6 months following the intervention by the Center for Survey Research in Bloomington.
- 8) Information will be stored in locked file cabinets in a locked research office and data stored on a database that is password protected. This database will be used for this study only.

D.5. Data Collection. The baseline interview by phone or electronic communication, which will occur during the verbal consent call or within 1 week if the women needs a more convenient time, will include questions about CRC and BC screening as well as questions for perceived risk, benefits, barriers, and self-efficacy. Sociocultural/demographic variables will be measured for subgroup comparisons. The computer program used to conduct telephone surveys will have the randomization scheme integrated into the program. When a baseline survey is completed, the computer program will provide the randomized group assignment to the research assistant. The research assistant will then provide instructions to the participant based on her randomized group assignment.

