Those randomized to the TIWeb or CSC intervention group will be told they will receive a TIWeb or CSC in the next week followed by data collection calls at four weeks and six months. Women randomized to the TIWeb plus CSC will be told they will receive access to TIWeb in the next week followed by the CSC about CRC or BC screening as well as data collection calls or electronic communication at 4 weeks and six months. The usual care group will be told they will receive telephone calls or electronic communication for data collection at 4 weeks and six months. At the 4-week interview, women will be queried about their receipt, recall, and use of the TIWeb and their recall of the CSC. At six months, women will be asked about their screening behaviors. Participants will be offered a \$20 gift certificate for each telephone survey they complete, for a total of \$60 per participant across the entire study. This small incentive compensates women for their time. **Table 1** contains a timeline of project activities.

D.6. Tailored Interactive Website (TIWeb).

The interactive program will operate from a computer. The specific

graphic design will be determined after Community Advisory Board (CAB) preference testing, but be similar to the sample screens provided in Appendix C. Control buttons will be large enough to be easily seen and will be clearly labeled for easy identification. The narrator will walk the viewer through every aspect of the program so that each woman can easily respond to data queries. The program will also be designed to allow a woman to stop the program at any given point and return later to that place in the program.

D.6.1. ITWeb Development:

Message libraries, tailoring algorithms, and the majority of the content that will be included in the proposed TIWeb and CSC have been

Figure 3. Flow of TIWeb Content for Group A (Non adherent to both CRC and BC)

[figure not shown]

Table 2. Messages for Screening by Stage

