The Center for Survey Research in Bloomington, by phone or electronically survey, will collect T1, T2, and T3 data and provide any technical assistance needed with the TIWeb. Participants who have questions about the TIWeb will be able to call a toll free number and a research assistant will call them back. The additional contact will be recorded for length of time and content and added as a covariate to final analysis. Extensive training will be required for all research assistants who collect data and provide technical help with the TIWeb. Research assistants who provide the CSC will be different individuals than those who do telephone interviews so that bias will not be introduced during data collection. Research assistants will be graduate students who will have an initial training session consisting of the following elements: 1) project rationale and overview, 2) detailed information about each intervention, 3) information about assisting women with the TIWeb, 4) delivery practice,

5) a detailed training manual, 6) an extensive question-and-answer period, and 7) breakout sessions for individualized role training. Although interviewers won't be blind to assignment, training will include extensive focus on standardizing the interviews.

D.10. Process Evaluation. Process evaluation for accrual will be determined by randomly selecting 25% of all accrual calls and rating callers using the evaluation checklist in **Appendix A**. Research assistants that receive below average on any criteria will be given additional training.

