¹²⁸⁾ and consistent with our previous research.^(9, 10) Construct validation for these stage measures was established via principal components analyses in an original and a replication study (involving 142 and 676 women, respectively).^(119, 128) Items for CRC and BC screening will determine whether participants: 1) have ever had a mammogram, FOBT, sigmoidoscopy, or colonoscopy; 2) have thought about having a mammogram, FOBT, sigmoidoscopy, or colonoscopy; or 3) intend to have any of these tests in the next six months. We will also ask participants if CRC or BC screening tests were for screening or diagnostic purposes and use their responses as a covariate. Screening and diagnostic procedures have different CPT codes.

Mammography and colonoscopy scheduling will be based on the location of the participating physician. The study team will be given a preferred list of sites to be scheduled as well as alternative sites if the patient chooses. Results of screenings will be sent immediately to the participant's primary health care provider as part of her routine care.

Past Screening History will be measured by self-reported items that assess CRC and BC screening tests women have had in the past 20 years or since the individual turned 50. Self-report will be the most feasible method to assess screening history since claims data may not accurately reflect all screening tests done in other health care settings or while they were covered by a different health insurance plan.

Participant Involvement: will be measured for the TIWeb and for the CSC. The participant involvement scale for TIWeb has 19 items that address interest and engagement in the program and its content. The items, piloted with 36 people (see Preliminary Studies), address ease of use, relevancy, information content, barriers, and general satisfaction. The Cronbach's alpha was 0.89 and 100% of people indicated that they found the program interesting, easy to use, easy to understand, and containing information that was important to them. The survey instrument can be found in **Appendix E**. There are 15 items that measure participant involvement in the CSC. Participants will be called within 4 weeks following intervention to obtain data on involvement with the intervention.

Beliefs about CRC or BC Screening

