Group A (nonadherent to CRC but adherent to BC screening guidelines)

Hypothesis 1- Efficacy Analysis: The differences in binary adherence across the four randomized arms will be tested initially with the chi-square test for a 2x4 cross-classification table (adherence by randomized intervention groups). Binary logistic regression analysis, with three dummy variables using usual care as the reference category, will be computed to study the effects of each intervention (TIWeb, CSC, TIWeb +CSC) versus usual care on adherence, while adjusting for any potentially confounding covariates. In addition, model contrasts will be specified to statistically compare each of the three intervention arms to the others. Since the intervention is delivered to the patient and not the provider, analysis of variation in CRC screening by practitioners will be limited. Outcomes of patients who share the same providers may be slightly more correlated than outcomes of patients from different providers. Thus, the within-provider correlation among patients will be assessed with variance components, and if necessary generalized estimating equations (GEE) will be used with logistic regression to account for the within-provider correlation. We will enter as independent variables into logistic models the following: randomized group membership and any demographic covariate (age, race, education, marital status, screening history, baseline stage of adoption, SF12 mental health component, SF12 physical health component) for which the randomized groups differ significantly at baseline using a liberal significance level of 0.20. We will also measure whether subjects report that their physicians have recommended the screening test in the past and the amount of out-of-pocket expense for screening and enter these as covariates. In addition to demographic variables, other potential covariates will be location of TIWeb intervention (use of a computer at home or elsewhere), and whether women in the TIWeb group needed technical help from the research assistant to use the TIWeb program. We plan to include screening history as a covariate in our analysis by using the total number of past screenings for each test since the participant turned 50. For analysis with mammography screening, one covariate will be included (total number of mammograms since age 50). For the analysis of CRC screening, two covariates will be included simultaneously in the models (total number of FOBTs since age 50, and "any previous endoscopic test" [yes/no]). The CRC screening analysis requires two covariates because a history of five FOBTs, for example, is not equivalent to one previous FOBT and one previous colonoscopy or sigmoidoscopy. All variables in the

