The effects on the ICERs of methods and parameter uncertainty will be assessed by one-way and/or multi-way sensitivity analysis. For example, ICERs may be sensitive to wage rates of key personnel and the overhead rates. Statistical uncertainty in the cost-effectiveness ratios will be assessed with 1,000 bootstrap samples. The outcome of each bootstrap sample will be expressed as a point on a scatter plot of incremental costs and percent screened and reflects the uncertainty arising from the model parameters. Scatter plots of the incremental costs and effects will be used to define the 95% confidence limits around the cost-effectiveness ratios.⁽¹⁴⁶⁾

Aim 3: Interaction analysis.

Hypothesis 1 Interactions: We will use interaction terms in the logistic regression models, developed above for analyses of Aim 1, to test whether intervention effects depend on knowledge, cancer screening beliefs, health status, demographic variables (age, race, education, and marital status), screening history, out-of-pocket costs for screening, baseline stage of adoption, provider recommendation, and participant involvement in the intervention. We will also test the interaction between each intervention and whether participants sought help through additional contact(s) with the research assistants. If an interaction is significant, we will use parameter estimates from the logistic regression model to estimate odds ratios for intervention effects at various levels or scores of the interacting covariates (e.g., within each race or site, or at various values, for example quartiles, of perceived barriers). Because many interactions will be tested, we will adjust for multiple comparisons (see below).

Hypothesis 2 Site Differences: We will compare screening adherence between the group of women who receive care in sites that have colonoscopy available with those who are not in such sites using logistic regression after adjusting for randomized group (usual care, TIWeb, CSC, and TIWeb + CSC).

Adjustment for multiple comparisons: Because many tests will be performed in Exploratory Aim 3, we will report p-values adjusted for multiple comparisons in the analyses, using the resampling step-down adjustment method of Westfall and Young,⁽¹⁴⁷⁾ which accounts for the dependence structure between related tests.

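### The Aim 1 adjusted model admits covariates that arise only after randomization and only in the TIWeb arms, so its arm odds ratios may not estimate the randomized effect

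*Combined protocol and SAP*

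**What the plan says.** D.13, Aim 1, Hypothesis 1 (Efficacy Analysis) specifies a logistic model with three arm indicators against usual care, contrasts among the intervention arms, and adjustment for covariates. After the baseline variables it states that "other potential covariates will be location of TIWeb intervention (use of a computer at home or elsewhere", together with "whether women in the TIWeb group needed technical help from the research assistant to use the TIWeb program". The adjusted odds ratios and their 95% confidence intervals are the estimates to be reported. The Group B text carries covariate adjustment over to the ordinal models.

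D.9, on calls for help with the website, is firmer: "The additional contact will be recorded for length of time and content and added as a covariate to final analysis". It does not name the model.

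On timing, D.5 states: "When a baseline survey is completed, the computer program will provide the randomized group assignment to the research assistant". Website access follows, and only in the TIWeb and TIWeb + CSC arms (D.1, D.8). Use is asked later: "At the 4-week interview, women will be queried about their receipt, recall, and use of the TIWeb and their recall of the CSC".

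Two other places bear on the point. In D.13, Aim 3, "We will use interaction terms in the logistic regression models, developed above for analyses of Aim 1" is followed by "We will also test the interaction between each intervention and whether participants sought help through additional contact(s) with the research assistants". D.11 adds: "We will also ask participants if CRC or BC screening tests were for screening or diagnostic purposes and use their responses as a covariate", without saying at which survey this is asked.

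**The concern.** Covariate adjustment in a randomized comparison is safe when the covariates are fixed before assignment. Where the website was used, and whether help was needed, are consequences of being assigned to it. A woman in usual care or CSC alone has neither, so these variables cannot be baseline confounders, which is the purpose D.13 gives for adjusting.

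No section says how the variables are coded outside the TIWeb arms, confines them to analyses within those arms, or names a model with baseline covariates only as primary. If they are left missing outside the TIWeb arms, a complete-case fit loses usual care and CSC, which an analyst would notice. If they are coded 0, the fit looks normal, but the TIWeb coefficient now refers to women with a zero on that variable (those who needed no help, for example) against all of usual care.

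At stake are the adjusted pairwise comparisons. D.12 sizes the trial to compare any two arms, and Hypothesis 1 is framed as controlling for baseline mammography adherence; both lead to this model's arm terms and contrasts.

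**Working it through.** **Inputs from the plan (D.12).** Six-month CRC adherence of 20% (usual care), 30% (TIWeb, called TIDVD in the table), 40% (CSC) and 55% (both), with 357 women per arm, Groups A and B combined. Two-sided alpha of 0.05 is assumed; the power table does not state it.

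**The plan's own figures.** A two-proportion calculation gives power 0.871 for TIWeb v usual care (plan .87) and 0.801 for CSC v TIWeb (plan .80). The logistic Wald version gives 0.866 and 0.798. The unadjusted TIWeb odds ratio is (0.30/0.70)/(0.20/0.80) = 1.71.

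**Assumptions not in the plan.** A fraction f of women in each TIWeb arm has the covariate equal to 1, with odds ratio k for adherence; it is 0 in the other two arms. Arm rates are held at the planned values by solving, in each TIWeb arm,

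(1 − f)·expit(a) + f·expit(a + ln k) = arm rate.

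The adjusted TIWeb odds ratio is then the odds expit(a)/(1 − expit(a)) in the TIWeb arm divided by 0.25, the usual-care odds. Example with f = 0.10, k = 2: women without help have adherence 28.4%, odds 0.397, and 0.397/0.25 = 1.59.

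**Technical help.** Power is by the Wald approximation. The false-positive rate is for TIWeb v usual care with no TIWeb effect (rates 20/20/40/40%).

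| Help prevalence | TIWeb OR, k = 2 | Power v usual care, k = 2 | False-positive rate, k = 2 | TIWeb OR, k = 0.5 | CSC v TIWeb power, k = 0.5 |
|---|---|---|---|---|---|
| 2% | 1.69 | 0.84 | 5.1% | 1.73 | 0.77 |
| 5% | 1.65 | 0.81 | 5.6% | 1.77 | 0.74 |
| 10% | 1.59 | 0.73 | 7.1% | 1.82 | 0.67 |
| 20% | 1.47 | 0.56 | 13.1% | 1.94 | 0.51 |

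With k = 1 the odds ratio stays at 1.71. Simulating 3,000 trials per setting with the likelihood ratio test that D.13 names, at k = 2, gives power 0.85/0.81/0.73/0.58 and false-positive rates of 4.5/5.7/7.0/13.4%.

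**Location.** D.13 does not say which category is coded 1. Take 80% home use and k = 1.25. In the TIWeb arm, adherence is then 30.9% at home and 26.4% elsewhere.

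- Home = 1: (0.2636/0.7364)/0.25 = 1.43, standard error 0.239, power 0.32.
- Elsewhere = 1: (0.3091/0.6909)/0.25 = 1.79, standard error 0.180, power 0.90.

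Part of the first loss is precision rather than bias. With k = 1 and home = 1 the odds ratio is 1.71, but the standard error rises from 0.176 to 0.235 and power is 0.63, because the covariate nearly duplicates TIWeb assignment.

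**Test purpose (D.11), only if asked about follow-up tests.** With a diagnostic yes/no code and any test as outcome, every woman coded diagnostic is adherent. The arm odds ratio then becomes [0.3(1 − d1)/0.7]/[0.2(1 − d0)/0.8], where d0 and d1 are the diagnostic shares of tests in usual care and TIWeb. It is 1.52 for d0 = 10%, d1 = 20%; 1.93 if these are reversed; and 1.71 if they are equal.

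**Aim 3.** Help contact can be non-zero only in two arms, so its main-effect column equals the sum of its products with those two arm indicators. The full set of terms cannot be estimated, and an interaction with CSC alone has no data.

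**The case against.** The strongest reply is that nothing commits the trial to the harmful model. D.13 calls the variables potential covariates and words them in terms of the TIWeb group, so a within-TIWeb reading is natural; D.9 does not say which final analysis it means. Harm requires that the variable be selected, coded 0 elsewhere and related to adherence. That is correct, and it is why the conclusion is that the odds ratios may be distorted. But D.13 places the variables in the paragraph defining the four-arm model, D.9 is not conditional, and no section imposes the safer reading.

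Help may also be rare. High-speed Internet is an eligibility criterion (D.2), and helpers are trained to give no extra education (Data Safety and Monitoring Plan). At 2–5% prevalence the shift is small, and with k = 1.25 it is negligible (1.71 to 1.69). This stands. Helped women may nevertheless differ from the rest even if the help itself does nothing.

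For location, mostly home use with elsewhere coded 1 does little harm: at 95% home use the odds ratio is 1.73 and power 0.88. Under the opposite code, the inflated standard error would be visible. Both points stand, but the plan does not choose the code.

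There are real safeguards. The initial 2x4 chi-square test, the unadjusted Group B tables and the ICERs on raw percentages are untouched, and Program Effectiveness states an intention-to-treat principle. The chi-square is a global test, however, and that principle appears under the cost-effectiveness aim; it does not restrict the Aim 1 covariates.

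The D.11 item may well concern screening history, in which case it is harmless.

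**Conclusion.** The concern holds. As written, the plan allows covariates that arise after assignment, and exist only in the TIWeb arms, into the model that yields the adjusted arm odds ratios; for help contact, D.9 commits to a final analysis that it does not name. The structural error follows from the text. Its size does not: it rests on assumed prevalence, association and coding of 0 outside TIWeb. Under those assumptions the effect ranges from negligible (rare help, or no association) to material (TIWeb odds ratio 1.47 instead of 1.71 and power 0.56 instead of 0.87 with help at 20% and k = 2). The location result is the more telling one, since an unstated coding choice moves the estimate between 1.43 and 1.79 on the same data.

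The figures use 357 per arm because D.12 now combines Groups A and B, although the D.13 efficacy text still sits under a Group A heading. The D.11 point depends on when test purpose is asked.

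**What to change.** - In D.13, limit the Aim 1 adjusted models, including the Group B ordinal models, to covariates measured before randomization, with baseline mammography adherence among them.
- Remove TIWeb location, technical help or help contact, and any follow-up test purpose from those models. Report them descriptively or in exploratory analyses within the TIWeb arms, and change D.9 to match.
- In D.11, state when test purpose is asked and which analysis uses it. Handle diagnostic tests by a sensitivity analysis of the outcome, counting and then not counting them.
- In Aim 3, restrict the help-contact and participant-involvement interactions to arms where the variable is defined, or present them as within-arm associations.

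The cost is plan wording only. The same data are collected, and the sample size is unchanged.

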*Consistency in intervention delivery is assured through the standardized programming used in the computer-assisted CSC and through taping and review of CSCs. The TIWeb guide the participant through all sections. The CSCs will be continuously recorded for quality assurance. Monthly taping of at least one TIWeb technical assistance session and T1, T2, and T3 interview for each interviewer will allow checks on consistency of performance. Taped interviews and CSC calls will be evaluated based on a checklist contained in **Appendix A**. Research assistants who are not delivering calls as instructed will be given additional training. Research assistants will address any unusual happenings during biweekly meetings. Decisions to modify procedures will be made jointly and documented. The research team will meet monthly to discuss any concerns with implementation of the protocol or collection of interview data. The principal investigators will meet weekly to refine the protocol and training procedures and to discuss ongoing issues.*

Table 6. Measurement of Outcomes: Stage and Adherence for BC and CRC

Stage	CRC Screening Average risk woman	CRC screening At higher risk because of family history	BC Screening
Precontemplation	Is nonadherent to national guidelines and does not intend to have one of the test options in next 6 months	Never had a colonoscopy or had one > 10 years ago and does not intend to have one in next 6 months	Never had a mammogram or had one \geq 15 mo. ago and does not intend to have one in next 6 months
Contemplation	Is nonadherent to national guidelines but intends to have one of the test options in next 6 months	Never had a colonoscopy or had one > 10 years ago and intends to have one in next 6 months	Never had or had mammogram more than 15 months ago but intends to have one in next 6 months
Action (Adherence to any CRC screening)	Had one of the test options since intervention	Had one of the test options since intervention	Had a mammogram since intervention
Action (Adherence to risk appropriate CRC screening)	Had one of the test options since intervention	Had a colonoscopy since intervention	Had a mammogram since intervention

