
logistic regression models will be tested using the likelihood ratio test.⁽¹⁴¹⁾ Adjusted odds ratios and profile-likelihood-estimated 95% confidence intervals for those odds ratios will be provided.

Analyses of stage of screening will be the same as analyses above for adherence, except that the binary outcome is advancement (from baseline) in stage of adoption for CRC screening guidelines. There are two possible stages of adoption at baseline (precontemplation and contemplation) and three possible stages at 6 months (precontemplation, contemplation, and action). Thus, there are four possible stage movements from baseline to 6 months (fall back one stage, remain the same, advance one stage, or advance two stages). However, data on a large sample in the Preliminary Studies demonstrated that, of 904 women followed to 9 months post-baseline, only 4% of women fell back one stage and only 6% advanced two stages; the majority either advanced one stage (50%) or remained the same (39%). Therefore, we will implement the outcome of stage change as a dichotomous variable: improvement (advance one or two stages) versus no improvement (remain the same or fall back one stage).

Group B (nonadherent to both CRC and BC screening guidelines)

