Hypothesis 1- Efficacy Analysis: Similar to the approach in Hypothesis 1 for **Group A**, screening adherence across the four randomized arms will be tested initially with the chi-square test for a 2x4 cross-classification table and then adjusting for covariates in logistic regression models. However, the statistical procedures will be generalized versions (Mantel chi-square and ordinal logistic regression) to accommodate an ordinal outcome. The three possible ordinal responses for the outcome are: 1) no adherence, 2) adherence to either CRC or BC screening, and 3) adherence to both CRC and BC screening. Specifically, we will perform: a) the Mantel chi-square test of linear trend and the Liu-Agresti ordinal odds ratio (the latter is a contingency-table-based statistic but assumes proportional odds) on a 2 x 3 cross-classification table (intervention group by ordinal adherence), and b) ordinal, instead of binary, logistic regression models. If the assumption of proportional odds is not satisfied, a more general logistic regression model, the generalized logit model, will be employed, and two odds ratios, instead of a single Liu-Agresti odds ratio, will be reported for the classification tables. Analyses of stage will be the same as for adherence, except the three possible ordinal responses would be based on improvement (from baseline) in stage of adoption: 1) no improvement in stage, 2) improvement in stage of either CRC or BC screening, and 3) improvement in stage of both CRC and BC screening. The Preliminary Studies show we have a great deal of experience analyzing outcomes of screening adherence and stage improvement, for both BC and CRC outcomes.

Aim 2: Analyses for cost effectiveness is described next. To conduct cost-effectiveness (CE) analysis of a cancer screening program, it is necessary to determine both the effectiveness of a given intervention (as measured by the achieved outcomes) and the costs of providing the intervention to both groups A and B. The cost-effectiveness analysis will be conducted from the perspective of both the provider and the participants.

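### Stage improvement is a different event for precontemplators and contemplators, so the planned intervention-by-baseline-stage interaction on that outcome partly reflects the definition rather than who benefits in screening

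*Combined protocol and SAP*

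**What the plan says.** Table 6 separates the two baseline stages by stated intention alone. An average-risk woman is in contemplation if she "Is nonadherent to national guidelines but intends to have one of the test options in next 6 months"; without that intention she is in precontemplation. Action is a completed test: "Had one of the test options since intervention". The intention comes from a survey item in D.11, on whether women "intend to have any of these tests in the next six months".

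D.13 (Aim 1, Hypothesis 1, stage analysis) notes that "There are two possible stages of adoption at baseline (precontemplation and contemplation) and three possible stages at 6 months". It then collapses movement: "we will implement the outcome of stage change as a dichotomous variable: improvement (advance one or two stages) versus no improvement". The justification is an earlier cohort of 904 women followed to 9 months, in which "only 4% of women fell back one stage and only 6% advanced two stages", 50% advanced one stage and 39% stayed the same. For Group B the same idea becomes a three-level outcome whose middle level is "improvement in stage of either CRC or BC screening".

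Baseline stage is on the Aim 1 covariate list, but it enters the model only if the arms differ on it at the 0.20 level.

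Aim 3, Hypothesis 1 adds interaction terms to the logistic models built for Aim 1. Its list of modifiers ends with "out-of-pocket costs for screening, baseline stage of adoption, provider recommendation, and participant involvement in the intervention". It does not say whether the baseline-stage interaction applies to adherence, to stage improvement, or to both. Aim 3 is labelled exploratory, and its p-values are to be adjusted by the Westfall-Young step-down method.

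**The concern.** On the stage outcome, the proposed modifier also fixes what counts as success. In precontemplators, improvement is a mixture of new intentions and completed tests. In contemplators it is completed tests only. An arm-by-baseline-stage term therefore compares effects on two different events.

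The natural reading of such a term is that the website or the call works better in one stage than in the other. Section C promises this kind of conclusion: it says the trial will show which intervention is more effective for subgroups and names stage of screening among the covariates. If the effect on screening is the same in both stages, a definitional interaction would point readers to contemplators as the women who benefit.

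**Working it through.** **The plan's own figures.** D.12 gives 6-month CRC adherence of 20%, 30%, 40% and 55% with 357 women per arm. Assume two-sided α = 0.05, which is not stated, and use

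power = Φ{(|p₁−p₂| − 1.96√(2p̄(1−p̄)/n)) / √((p₁(1−p₁)+p₂(1−p₂))/n)}.

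This gives 0.871 for 20% v 30%, 0.801 for 30% v 40%, 0.981 for 40% v 55%, and above 0.999 for the other pairs. The stated values are .87, .80, .98 and .99, so the planning rates are reproduced. The plan gives no power figure for stage improvement or for interactions.

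**Why the odds ratio shrinks.** Let p be the chance that a precontemplator completes a test, with odds o = p/(1−p). Let g be the chance that an untested precontemplator states an intention at 6 months. Then

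- P(improve) = p + (1−p)g
- odds of improving = (o + g)/(1 − g)
- odds ratio for improving = (o₁ + g)/(o₀ + g), if g is the same in both arms.

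The odds ratio for testing is o₁/o₀. With g > 0 and o₁ > o₀, the improvement odds ratio is closer to 1. With o₁ = o₀ both equal 1, so there is no artefact without an arm effect. In contemplators, improving is the same as testing, so the odds ratio stays at o₁/o₀.

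**Worked example.** Assumptions: 60% precontemplators, g = 0.20, contemplator-to-precontemplator odds ratio for testing 3, overall testing 20% v 55%, and the same arm odds ratio in both stages.

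| | Usual care | Intervention | Odds ratio |
|---|---|---|---|
| Precontemplators, tested | 12.9% | 44.6% | 5.4 |
| Contemplators, tested (= improved) | 30.7% | 70.7% | 5.4 |
| Precontemplators, improved | 0.129 + 0.871×0.2 = 30.3% | 0.446 + 0.554×0.2 = 55.6% | 2.9 |

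Check on the overall rates: 0.6×12.9 + 0.4×30.7 = 20%, and 0.6×44.6 + 0.4×70.7 = 55%. An identical effect on screening appears as 2.9 v 5.4.

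**How often the test rejects.** Simulated two-arm trials, 357 per arm, logistic model with arm, baseline stage and their product; precontemplator share 40-60%, g = 0.10-0.20, testing odds ratio 3 between stages (all assumed):

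| Adherence contrast | Stage improvement, unadjusted | Adherence, unadjusted |
|---|---|---|
| 20% v 30% | 9-16% | about 5% |
| 20% v 40% | 15-36% | about 5% |
| 20% v 55% | 22-58% | about 5% |

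Aim 3 lists 13 modifiers, counting the four demographic variables separately and including extra contact with research assistants. With 0.05/13 as a Bonferroni stand-in for Westfall-Young, the stage-outcome rates across these cells are about 1-24%, against 0.3-0.4% for adherence.

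**A second set-up.** All four arms at the planned rates, equal testing rates in the two stages, 3-df likelihood-ratio test, precontemplator share 30-70%: unadjusted rejection is about 9% (g = 0.1), 17-19% (0.2), 25-30% (0.3) and 41-49% (0.5). With g = 0, which is the adherence outcome, it is about 5%. With smaller effects (20/25/30/35%) and a 50% share it is 7%, 14% and 20% at g = 0.1, 0.3 and 0.5.

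**No arm effect.** With 20% testing in every arm and g = 0.1-0.5, the interaction test rejects in 4.4-5.5% of trials. The overall four-arm comparison of improvement (g = 0.1 and 0.3) rejects in 4.9-5.2%. Both are nominal.

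**The case against.** Several points on the other side are sound.

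- A reader might infer that unreliable intention answers alone produce false interactions or false arm effects. They do not: without an arm effect all rejection rates are nominal. The artefact needs a real effect on screening. That is, however, the scenario on which the trial is powered.
- A reader might infer that the stage outcome has no verification at all. Only intention is unverified; D.11 checks completed tests against claims and chart audit at 6 months.
- Aim 3 is exploratory and multiplicity-adjusted, which cuts the rejection rates considerably. The adjustment limits chance findings, though. It does not correct an odds ratio that is displaced by the definition, and D.13 would report odds ratios at levels of the modifier when an interaction is significant.
- The 4% fall-back in the earlier cohort is not a measure of answer noise, because women can change their minds, and movement there was strongly forward. The flip rate, stage mix and testing odds ratio used here are assumptions. Any figure for noise-driven improvement in Group B would also need the two intention items to be independent, while the protocol says the two screening behaviours are correlated.
- Section A deliberately values movement from precontemplation to contemplation, and different odds ratios for advancing a stage are true of that outcome. They mislead only when read as differences in screening benefit. That supports keeping the outcome and tabulating its parts.
- Aim 3 may have been meant for adherence alone. The text does not say so.

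**Conclusion.** The concern holds for one analysis: the intervention-by-baseline-stage interaction on stage improvement. With equal screening odds ratios in both stages and intention-only moves equal across arms, that test rejects too often: about 9-58% unadjusted over the contrasts and assumptions above, and about 1-24% with the Bonferroni stand-in. The stratum odds ratios stay distorted whatever the p-value. The size depends on the assumed precontemplator share, flip rate and testing odds ratio, none of which the documents give. It is smallest for the 20% v 30% contrast. If the interventions also change stated intention, the precontemplator odds ratio would shift differently, but the two stages would still be measured on different events.

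The documents do not support a wider reading. The randomised comparison of stage improvement between arms remains valid for that outcome as defined, and adherence, which drives the sample size, is unaffected. The point is worth correcting before analysis, but it does not threaten the primary conclusion.

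**What to change.** 1. In D.13, Aim 3, Hypothesis 1, state that the intervention-by-baseline-stage interaction is tested on completed screening (adherence) only, and drop it for stage improvement.
2. In D.13, Aim 1, always include baseline stage as a covariate in the stage-improvement model, instead of only when the arms differ on it at the 0.20 level.
3. Report, by arm and baseline stage, how many women reached contemplation and how many reached action; in Group B, do this for each test.

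The cost is a change of wording, slightly more tabulation and one fewer exploratory interaction. No new data are needed. The prespecified dichotomy can stay. An ordinal model for 6-month stage is at most an optional sensitivity analysis: it brings a proportional-odds assumption, and in simulation it lost about 4-9 points of power when only testing moved.
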